3.3 Exploratory Objectives

1. **Objective:** To assess the expression of PD-1, PD-L1 on MPN cells and supporting stromal cells in the bone marrow and blood of patients being treated with pembrolizumab.
2. **Objective:** to evaluate whether treatment with pembrolizumab affects various immune pathways in the bone marrow of patients with advanced forms of myeloproliferative neoplasms.

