4.2.4 Rationale for Endpoints

4.2.4.1 Efficacy Endpoint

Primary endpoint:

1. The proportion of treated MF-CP patients (primary cohort) that achieve at least a clinical improvement (CI, PR, CR) by combined European Leukemia Net – International Working Group (ELN-IWG) criteria (Table 5) after 6 cycles of pembrolizumab therapy.

Secondary endpoint:

1. The proportion of treated MPN-AP/BP patients (exploratory cohort) that achieve at least a complete morphologic remission of the leukemic blasts (CR, Cri) by Acute Myeloid Leukemia Response Criteria (Table 6A) within 6 cycles of pembrolizumab therapy.
2. The proportion of treated MPN-AP/BP patients (exploratory cohort) that achieve at least an acute leukemia response-partial (ALR-P, ALR-C, CCR, CMR) using published consensus criteria by Mascarenhas et al. (Table 6B) within 6 cycles of pembrolizumab therapy.

4.2.4.2 Exploratory Endpoints:

1. Assess expression of PD-1/PD-L1 on peripheral blood PB-MNCs, T-cells and CD34+ cells by flow cytometry
2. Assess expression of PD-1/PD-L1 on bone marrow CD34+cells and supporting stromal cells by immunohistochemical staining
3. Assess PD-1/PD-L1 DNA methylation status by bisulfite-sequencing assay
4. Assess status and change in PD-1/PD-L1 expression with response to therapy.
5. Assess changes in driver mutation burden (*JAK2V617F*, *MPLW515L/K*, *CALR*) in granulocytes from treated patients at diagnosis, after 6 cycles and at 1 year of pembrolizumab therapy using the rapid heme panel for next generation sequencing at Brigham and Women's hospital and correlate with response to therapy.
6. Evaluate changes in immune response gene expression profile as well as tumor microenvironment in bone marrow biopsy specimens using nanostring technology after 6 cycles of treatment with pembrolizumab.

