4.2.4.4 Biomarker Research

Immunotherapy as a target in MPN has not been extensively studied. As such, an important component of this study will be to gain better understanding of markers that predict outcome and response to PD-1 therapy.

1. Biomarker: Assess expression of PD-1/PD-L1 on peripheral blood PB-MNCs, T-cells and CD34+cells by flow cytometry:

Up-regulated PD-1 expression on peripheral blood MNCs and PD-L1 on MPN CD34+cells provides an inappropriate immune tolerance signal allowing for disease progression. Pre-clinical data suggests that PD-1 and PD-L1 are upregulated in patients with MDS and AML, especially in those who have received prior treatment. As part of this clinical trial we will test PD-1 and PD-L1 expression in circulating T-cells and tumor cells, respectively, to evaluate if expression of these molecules correlates with disease status and response to treatment.

Expected result: PD-1 expression is up-regulated on PB MNC and T-cells and PD-L1 is up-regulated on MPN HSC from patients enrolled on this trial at baseline.

Assay: Expression of PD-1 and PD-L1 will be measured by flow cytometry on cells from the peripheral blood of treated patients at baseline and at the start of cycle 3 (9 weeks).

2. Biomarker: Assess expression of PD-1/PD-L1 on bone marrow CD34+cells and supporting stromal cells by immunohistochemical staining

Up-regulated PD-1 expression on peripheral blood MNCs and PD-L1 on MPN CD34+cells provides an inappropriate immune tolerance signal allowing for disease progression. Pre-clinical data suggests that PD-1 and PD-L1 are upregulated in patients with MDS and AML, especially in those who have received prior treatment. As part of this clinical trial we will test PD-1 and PD-L1 expression in circulating T-cells and tumor cells, respectively, to evaluate if expression of these molecules correlates with disease status and response to treatment. Expression of CD45 surface marker will be evaluated in parallel with PD-1 and/or PD-L1 expression to differentiate between stromal (CD45 positive) and hematopoietic cells (CD45 positive) within the bone marrow.

Expected result: PD-1 expression is up-regulated on PB MNC and T-cells and PD-L1 is up-regulated on MPN HSC from patients enrolled on this trial at baseline.

Assay: Expression of PD-1 and PD-L1 will be measured by immunohistochemistry on bone marrow.

3. Biomarker: Assess PD-1/PD-L1 DNA methylation status by bisulfite-sequencing assay

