8.2.4 Analysis of Exploratory Endpoints

8.2.4.1 Biomarker: Assess expression of PD-1/PD-L1 on peripheral blood PB-MNCs, T-cells and CD34+cells by flow cytometry:

To assess expression of PD-1/PD-L1 on peripheral blood PB-MNCs, T-cells and CD34+cells, median fluorescence intensity (MFI) and the percentage of cells expressing each antigen within a gate will be estimated for each sample by flow cytometry. If there are no expression levels equal to 0 among the samples, geometric means of MFIs and percentage of cells will be reported at baseline and at the start of cycle 6. The change in geometric mean MFIs/percentage of cells from baseline to end of cycle 6 will be reported as the ratio of geometric means and tested for difference from one using a paired t-test on log transformed data. If, however, there are expression levels equal to 0, median and interquartile range of MFIs/percentage of cells will be reported at baseline and end of cycle 6 treatment. Difference between median MFIs/percentage of cells from baseline to end of cycle 6 will be tested using a Wilcoxon Signed Rank test.

8.2.4.2 Biomarker: Assess expression of PD-1/PD-L1 on bone marrow CD34+cells and supporting stromal cells by immunohistochemical staining:

To assess expression of PD-1/PD-L1 on bone marrow CD34+ cells and supporting stromal cells by immunohistochemical staining, percentages of PD-L1 and PD-1 positive tumor cells and staining intensity will be evaluated for each sample. Staining intensity will be scored

Product: MK-3475

Protocol/Amendment No.:

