considering 0 as negative or trace, 1 as weak, 2 as moderate and 3 as high. A semi-quantitative approach will be used to generate an H-score for each tissue core defined as the percentage of stained cells (0–100%) multiplied by the dominant intensity pattern of staining ranging from 0 to 3. The overall semi-quantitative H-score will range from 0 to 300. If there are no H-scores of 0 among the samples, geometric means of H-scores will be reported at baseline and at the end of cycle 6 treatment. The change in geometric mean H-scores from baseline to end of cycle 6 will be reported as the ratio of geometric means and tested for difference from one using a paired t-test on log transformed data. If, however, there are H-scores of 0, median and interquartile range of H-scores will be reported at baseline and following cycle 2 treatment. Difference between median H-scores from baseline to end of cycle 6 will be tested using a Wilcoxon Signed Rank test. In addition to the semi-quantitative H-score approach, a dichotomous variable indicating expression positivity will be created. In the absence of any standardized scoring system, all cases with staining intensity ≥ 2 in more than 5% of tumor cells will be considered as positive, similarly to previous studies (Antonia *et al.*, 2013; Grosso *et al.*, 2013; Soria *et al.*, 2013). McNemar's test will be used to test for a change in the percentage of patients with positive PD-1/PD-L1 expression from baseline to the start of cycle 6 follow-up.

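### Marrow immunohistochemistry: as written, the plan yields no stromal PD-1/PD-L1 value, and its H-score turns on an undefined dominant intensity

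*Combined protocol and SAP*

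**What the plan says.** **What is to be estimated.** Exploratory objective 1 (section 3.3) is "To assess the expression of PD-1, PD-L1 on MPN cells and supporting stromal cells in the bone marrow and blood". The second exploratory endpoint (section 4.2.4.2) is "Assess expression of PD-1/PD-L1 on bone marrow CD34+cells and supporting stromal cells by immunohistochemical staining". The heading of SAP section 8.2.4.2 names the same two cell types.

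**How compartments are told apart.** Section 4.2.4.4, item 2, has CD45 read alongside PD-1 and PD-L1 "to differentiate between stromal (CD45 positive) and hematopoietic cells (CD45 positive) within the bone marrow". Section 8.2.4.2 does not mention CD45.

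**What is scored.** Section 8.2.4.2 states that "percentages of PD-L1 and PD-1 positive tumor cells and staining intensity will be evaluated for each sample". Intensity is graded "considering 0 as negative or trace, 1 as weak, 2 as moderate and 3 as high". An H-score is then formed "for each tissue core defined as the percentage of stained cells" and "multiplied by the dominant intensity pattern of staining ranging from 0 to 3", with a stated range of 0 to 300.

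**How it is analyzed.** If no H-score is 0, the change from baseline to the end of cycle 6 is a ratio of geometric means, tested by a paired t-test on logs. If there are zero scores, medians are reported and a Wilcoxon signed rank test is used. Separately from the H-score, a positivity variable is created: "all cases with staining intensity ≥ 2 in more than 5% of tumor cells will be considered as positive". McNemar's test is applied to it.

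**The concern.** There are two problems.

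First, stromal expression is named in the objective, the endpoint and the analysis heading, yet no step in the plan produces it. The marker meant to separate stroma from hematopoietic cells has the same value in both, and the scoring text never asks for a stromal reading.

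Second, the H-score compresses a distribution of intensities into one category. When two categories are close in frequency, a trivial difference between cores, or between two readings of the same core, can change the multiplier. The change is analyzed as a ratio on the log scale, so such a flip enters the reported quantity directly. The plan does not say whether unstained cells compete for the dominant category, and that choice decides which cores score 0 and therefore which test is run.

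At stake is whether the trial can answer the stromal part of its own exploratory question, and whether a reported change in H-score reflects a change in staining.

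**Working it through.** **1. Is there a route to a stromal value?**

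| Step | Source | What it gives for stroma |
|---|---|---|
| Separation rule | 4.2.4.4, item 2 | CD45 positive, the same label as hematopoietic cells |
| Cells evaluated | 8.2.4.2 | Tumor cells |
| H-score, first factor | 8.2.4.2 | Stained cells in the core, compartment not stated |
| Positivity | 8.2.4.2 | Tumor cells |
| Marrow flow cytometry | Table 8, row 2 | Aspirate mononuclear cells are collected, but 8.2.4.1 analyzes peripheral blood and 8.2.4.2 only immunohistochemistry |

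No row yields a stromal number. The H-score denominator also differs from that of the rest of the section, or is undefined.

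**2. The stated range.** H = (percent stained) × (dominant intensity). The minimum is 0 and the maximum is 100 × 3 = 300, so the SAP's range is reproduced. The weighted form, H = 1 × %1+ + 2 × %2+ + 3 × %3+, also runs from 0 to 3 × 100 = 300.

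**3. Reading A: dominant is the most frequent intensity among stained cells.** The cores are illustrative. The documents give no intensity distribution.

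| Core | 1+ | 2+ | 3+ | Stained | Dominant | SAP H | Weighted H |
|---|---|---|---|---|---|---|---|
| A | 30% | 0% | 29% | 59% | 1 | 59 × 1 = 59 | 30 + 87 = 117 |
| B | 29% | 0% | 30% | 59% | 3 | 59 × 3 = 177 | 29 + 90 = 119 |

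One percentage point of cells has moved. The ratio is 177/59 = 3.0 for the SAP score and 119/117 = 1.02 for the weighted score. On the log scale the changes are ln 3 = 1.10 and ln(119/117) = 0.017. Over all whole-percent splits with a unique dominant category, 3.0 is the largest ratio that a one-percentage-point move can produce. It needs a near tie of 1+ and 3+, with 2+ less frequent. Flips between 1+ and 2+ give 2.0, and flips between 2+ and 3+ give 1.5.

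For scale, suppose all 24 primary-cohort patients have paired scores. One such flip in one patient multiplies the reported ratio of geometric means by 3^(1/24) = exp(1.0986/24) = 1.05.

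**4. Reading B: dominant is the most frequent category over all cells, with 0 included.** Take a core with 55% negative and 45% at 2+.

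- SAP H = 45 × 0 = 0.
- Weighted H = 2 × 45 = 90.
- Positivity: 45% at intensity 2 or above exceeds 5%, so the core is positive.

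The same core has H = 0 and a positive call, and its zero moves the analysis from the paired t-test to the Wilcoxon test. Under Reading A it scores 45 × 2 = 90.

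**5. The readings must not be mixed.** Under Reading B, cores A and B each have 100 − 59 = 41% unstained. Category 0 is then dominant in both and both score 0, so the tripling disappears. Under Reading A the 55%/45% core does not score 0. Each reading has its own defect, and the plan does not say which applies.

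**The case against.** The case for leaving this alone runs as follows. The CD45 sentence is evidently a one-word slip, since its purpose is to differentiate. The SAP calls its H-score semi-quantitative, and percent times intensity is a matter of index choice. The threefold change needs an unusual near tie. The result is exploratory.

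Much of this stands, and it rules out several stronger readings that a reader might infer:

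- **That one step on the 0–3 intensity scale triples the score.** It does not. With percent stained fixed, it multiplies a non-zero score by 2.0 (1 to 2) or 1.5 (2 to 3). The unit in the example is one percentage point of cells.
- **That category flips will drive the paired result.** The documents give no distribution from which to predict how often near ties occur. Flips can distort the result; no more can be said.
- **That positivity cannot be obtained.** Any whole-number H from 10 to 100 is compatible with either call (H = 41 arises from 41% all at 1+, and from 21% at 1+ with 20% at 3+). But the SAP creates positivity as a separate variable and does not derive it from H. It is available if percentages at each intensity are recorded. The SAP does not say whether they are, so this is missing detail, not an impossibility.
- **That only tumor cells are scored, or that exploratory objective 1 fails as a whole.** The H-score refers to stained cells, and the objective also covers MPN cells and blood. Only the stromal part lacks a route.

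What the objection does not remove: correcting the CD45 word still leaves 8.2.4.2 without a stromal score, Table 8's marrow flow cytometry has no analysis in section 8 that would supply one, and the dominant category is undefined under a score that misbehaves on either reading.

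**Conclusion.** The point holds in two parts. As written, the plan gives no stromal PD-1/PD-L1 value, although the objective and endpoint ask for one. This follows from the text alone and needs no assumption.

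The H-score is unstable and ambiguous. Among stained cells, it can change threefold (59 to 177) where a weighted score changes by 2%. Over all cells, it can be 0 for a core with 45% of cells at 2+ that meets the positivity rule. These figures rest on illustrative cores and on one reading of dominant at a time. They show what the rule permits, not how often it will happen.

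The matter is worth correcting because the repair is cheap, but its reach is limited to an exploratory biomarker. Nothing here bears on the primary endpoint, the stage 1 decision or the sample size.

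**What to change.** 1. In section 4.2.4.4, item 2, make the two CD45 labels differ: stromal negative and hematopoietic positive, for the sponsor to confirm.
2. In section 8.2.4.2, score the hematopoietic/tumor and stromal compartments separately, and state the denominator for each percentage. Say how the tumor-cell reading relates to the CD34+ cells named in the endpoint.
3. For each core and compartment, record the percentage of cells at 0, 1+, 2+ and 3+.
4. Define H = 1 × %1+ + 2 × %2+ + 3 × %3+. The range stays 0 to 300, no dominant category is needed, and a zero then occurs only when no cell stains at 1+ or above.
5. Take the existing positivity rule from the same record: %2+ plus %3+ greater than 5%.

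The cost is wording in the protocol and SAP, a revised scoring form, and slightly more scoring by the same reader on the same slides. No new samples or patients are needed.

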5.0 METHODOLOGY

5.1 Entry Criteria

5.1.1 Diagnosis/Condition for Entry into the Trial

This trial is targeting patients with advanced forms of myeloproliferative neoplasms (MPNs). This will include patients with myelofibrosis (MF) in chronic (CP), accelerated (AP), and blast phase (BP) disease. Patients with other MPNs such as essential thrombocythemia (ET) or polycythemia vera (PV) will be eligible if they have AP/BP disease. Patients with MF will include those with primary myelofibrosis (PMF) as well as post essential thrombocythemia (post-ET) or polycythemia vera (post-PV) myelofibrosis. MF-CP patients will be required to have survival risk scores associated with advanced disease (intermediate-2/high) by the established Dynamic International Prognostic Scoring System (DIPSS). Patients with MF-CP will have had to have been previously treated with ruxolitinib and either had a suboptimal response or been intolerant as determined by the investigator, or be ineligible for ruxolitinib treatment as determined by the treating investigator. Patients with MPN-AP/BP will have had to have been previously treated with a hypomethylating agent such as decitabine or azacytidine and have progressive or resistant disease as determined by the treating investigator. In all cases the subject must either not be eligible for hematopoietic stem cell transplant option or be unwilling to pursue this potentially curative treatment option.

5.1.2 Subject Inclusion Criteria

In order to be eligible for participation in this trial, the subject must:

1. Be willing and able to provide written informed consent/assent for the trial.
2. Be ≥ 18 years of age on day of signing informed consent.
3. Must have a diagnosis of chronic phase (CP) (defined as peripheral blood and bone marrow $<10\%$ blasts) primary myelofibrosis (PMF) or post essential thrombocythemia (post-ET) or polycythemia vera (post-PV) myelofibrosis by World Health Organization (WHO) criteria **OR** a diagnosis of a myeloproliferative neoplasm in accelerated/blast phase (MPN-AP/BP) defined as either a peripheral blood or bone marrow with $\geq 10\%$ blasts
4. If the diagnosis is MF-CP, must have Dynamic International Prognostic Scoring System (DIPSS) intermediate-2/high risk disease and either be intolerant/resistant to ruxolitinib as determined by the treating investigator or ineligible for ruxolitinib therapy as determined by the treating investigator (see Appendix 12.3)
5. If the diagnosis is MPN-AP/BP, must have progressive/resistant disease after treatment with a DNMT1 inhibitor therapy (azacytidine, decitabine) as determined by the treating investigator
6. Either not eligible or unwilling to proceed with hematopoietic stem cell transplantation (HSCT)
7. Have a performance status of 0 or 1 on the ECOG Performance Scale.
8. Demonstrate adequate organ function as defined in Table 1, all screening labs should be performed within 28 days of treatment initiation.

Table 1. Adequate Organ Function Laboratory Values

System	Laboratory Value
Hematological	
Absolute neutrophil count (ANC)	≥ 500 /mCL
Platelets	$\geq 25,000$ / mCL
Renal	
Serum creatinine OR Measured or calculated ^a creatinine clearance (GFR can also be used in place of creatinine or CrCl)	≤ 1.5 X upper limit of normal (ULN) OR ≥ 60 mL/min for subject with creatinine levels > 1.5 X institutional ULN
Hepatic	
Serum total bilirubin ^b	≤ 1.5 X ULN OR
	Direct bilirubin \leq ULN for subjects with total bilirubin levels > 1.5 ULN

AST (SGOT) and ALT (SGPT)	$\leq 2.5 \times \text{ULN}$ OR $\leq 5 \times \text{ULN}$ for subjects with liver metastases
Coagulation	
International Normalized Ratio (INR) or Prothrombin Time (PT)	$\leq 1.5 \times \text{ULN}$ unless subject is receiving anticoagulant therapy as long as PT or PTT is within therapeutic range of intended use of anticoagulants
Activated Partial Thromboplastin Time (aPTT)	$\leq 1.5 \times \text{ULN}$ unless subject is receiving anticoagulant therapy as long as PT or PTT is within therapeutic range of intended use of anticoagulants
^a Creatinine clearance should be calculated per institutional standard.	
^b unless due to Gilbert's disease or hemolysis	

9. Female subject of childbearing potential should have a negative urine or serum pregnancy within 72 hours prior to receiving the first dose of study medication. If the urine test is positive or cannot be confirmed as negative, a serum pregnancy test will be required.
10. Female subjects of childbearing potential should be willing to use 2 methods of birth control or be surgically sterile, or abstain from heterosexual activity for the course of the study through 120 days after the last dose of study medication (Reference Section 5.7.2). Subjects of childbearing potential are those who have not been surgically sterilized or have not been free from menses for > 1 year.
11. Male subjects should agree to use an adequate method of contraception starting with the first dose of study therapy through 120 days after the last dose of study therapy.

5.1.3 Subject Exclusion Criteria

The subject must be excluded from participating in the trial if the subject:

1. Is currently participating and receiving study therapy or has participated in a study of an investigational agent and received study therapy or used an investigational device within 4 weeks of the first dose of treatment.
2. Is or has an immediate family member (e.g., spouse, parent/legal guardian, sibling, or child) who is investigational site or sponsor staff directly involved with this trial, unless prospective IRB approval (by chair or designee) is given allowing exception to this criterion for a specific subject
3. Has a diagnosis of immunodeficiency or is receiving systemic steroid therapy or any other form of immunosuppressive therapy within 7 days prior to the first dose of trial treatment.
4. Has a known history of active TB (Bacillus Tuberculosis)

5. Hypersensitivity to pembrolizumab or any of its excipients.
6. Has had a prior anti-cancer monoclonal antibody (mAb) within 4 weeks prior to study Day 1 or who has not recovered (i.e., \leq Grade 1 or at baseline) from adverse events due to agents administered more than 4 weeks earlier.
7. Has had prior chemotherapy (except hydroxyurea), targeted small molecule therapy, or radiation therapy within 2 weeks prior to study Day 1 or who has not recovered (i.e., \leq Grade 1 or at baseline) from adverse events due to a previously administered agent.
 - Note: Subjects with \leq Grade 2 neuropathy are an exception to this criterion and may qualify for the study.
 - Note: If subject received major surgery, they must have recovered adequately from the toxicity and/or complications from the intervention prior to starting therapy.
8. Has a known additional malignancy that is progressing or requires active treatment. Exceptions include basal cell carcinoma of the skin or squamous cell carcinoma of the skin that has undergone potentially curative therapy or in situ cervical cancer.
9. Has active autoimmune disease that has required systemic treatment in the past 2 years (i.e. with use of disease modifying agents, corticosteroids or immunosuppressive drugs). Replacement therapy (eg., thyroxine, insulin, or physiologic corticosteroid replacement therapy for adrenal or pituitary insufficiency, etc.) is not considered a form of systemic treatment.
10. Has known history of, or any evidence of active, non-infectious pneumonitis.
11. Has an active infection requiring systemic therapy.
12. Has a history or current evidence of any condition, therapy, or laboratory abnormality that might confound the results of the trial, interfere with the subject's participation for the full duration of the trial, or is not in the best interest of the subject to participate, in the opinion of the treating investigator.
13. Has known psychiatric or substance abuse disorders that would interfere with cooperation with the requirements of the trial.
14. Is pregnant or breastfeeding, or expecting to conceive or father children within the projected duration of the trial, starting with the pre-screening or screening visit through 120 days after the last dose of trial treatment.
15. Has received prior therapy with an anti-PD-1, anti-PD-L1, or anti-PD-L2 agent. "Anti-CD137 or anti-Cytotoxic T-lymphocyte-associated antigen-4 (CTLA-4) antibody

(including ipilimumab or any other antibody or drug specifically targeting T-cell co-stimulation or checkpoint pathways)

16. Has a known history of Human Immunodeficiency Virus (HIV) (HIV 1/2 antibodies).
17. Has known active Hepatitis B (e.g., HBsAg reactive) or Hepatitis C (e.g., HCV RNA [qualitative] is detected).
18. Has received a live vaccine within 30 days of planned start of study therapy.

Note: Seasonal influenza vaccines for injection are generally inactivated flu vaccines and are allowed; however intranasal influenza vaccines (e.g., Flu-Mist®) are live attenuated vaccines, and are not allowed.

